5.2. Institutional Review Board

5.3 Study Objectives

Primary Objective

- a. The primary objective is to evaluate the effects of inhaled nasal sodium pyruvate (N115) in patients with confirmed COVID-19 or flu infections by determining changes in the duration of an active infection by PCR from nasal.
 Secondary Objective
- **a.** The second objective is to evaluate the ability of the inhaled nasal sodium pyruvate therapy in subjects with COVID-19 or flu infections to improve symptoms by the use of a patient diary and by collecting periodic vital signs, especially body temperature, blood pressure and pulse/Ox.

5.4. Study Design Overview

Individuals that are symptomatic for COVID19/influenza will initially be tested by Dynamic DNA Labs or Trinity Healthcare (Screening Visit). If positive for COVID19/influenza, patient will then be solicited for participation in the trial within 24 hours. After signing Informed Consent, women of child-bearing age will provide a urine sample to test for pregnancy. They will be randomly assigned to either the placebo or drug groups in a double blinded fashion and be given a data logbook, or clinical app for their phone, in which they will record the number of coughs and other flu-like symptoms they experience each day. Patients will be contacted by phone and/or sent reminders through a clinical phone app every two days to review symptoms and protocol compliance and patients will be tested via nasal swab every other day. This will continue every other day until the subject tests negative for COVID-19/ influenza (which is

defined as a 2-Log reduction in virus titer or less than 1000 copies of viral RNA) or 14 days, whichever comes first. Personnel collecting swabs will wear N95 mask and face shield, disposable examination gloves and disposable gown while collecting nasal swabs from patients. Samples will be collected outdoors, weather permitting, or in a well ventilated room in inclement weather.

6.0. The criteria for patient selection and for exclusion of patients, and an estimate of the number of patients to be studied.

6.1. Subject Selection

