6.4 Inclusion of Women and Minorities

Every attempt will be made to include all genders, and minorities that present with an active COVID-19 or flu infection that are not exempted due to exclusion criteria.

7.0. A Description Of The Design Of The Study, Including The Kind Of Control Group To Be Used, If Any, And A Description Of Methods To Be Used To Minimize Bias On The Part Of Subjects, Investigators, And Analysts.

7.1. Assignment Of Subject Number And Randomization

This is a placebo controlled double blinded trial. Upon enrollment, each subject will be sequentially issued a unique subject number starting at 100. Once a number has been assigned to a subject, it cannot be re-assigned to another subject. Subjects will be encouraged to complete the study, although they may withdraw at any time without prejudice. Termination will be reported to the sponsor in a timely manner. Details of the reason(s) why a subject is dropped from the study will be documented. Enrollment will continue until the number of subjects specified in the protocol has been attained. The data from all subjects that have been given a study compound will be retained for analysis.

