7.3.1. Pre-study Visit

A pre-study visit will occur and the eligibility of the subject for inclusion determined. COVID19 or influenza positive patients will sign an Informed Consent (paper or eConsent), and a list of current medications will be taken. Urine samples from child-bearing aged women will be collected and analyzed for pregnancy (or last menstrual cycle recorded). During this visit, any flu-like symptoms will be noted, temperature, Pulse/Ox and blood pressure will also be measured. During this pre-study visit, the patients are to continue with their normal therapy, if any.

7.3.2. Study Visit 1

Only COVID19 or influenza single positive subjects meeting enrollment criteria will be enrolled after review of health information collected in the pre-study visit. The correct use of the N115 sodium pyruvate nasal spray will be demonstrated to COVID-19 or influenza infected subjects, and the subjects that have been confirmed to have an infection will administer their first dose while monitored in the clinic or via telehealth. (Nasal spray can be delivered to patient at time of telehealth visit by currier). The patients will be told to spray each nostril three times, three times per day: morning, mid-day, and evening. Patients will also be instructed on filling out the Daily Data Log form or in the use of the clinical symptoms app, which will be used to record administration of the drug doses, any flu-like symptoms, and any perceived adverse events.

7.3.3 Study Visit 2 etc.

At home or on-site follow-up visits will occur every two days after Study Visit 1. During this visit, a nasal swab will be taken to determine if the patient still has an active infection. Temperature, Pulse/Ox and blood pressure will also be examined during these visits. Study monitors will review the Daily Data Log form/ Clinical app and compliance with study protocol of N115 administration will be reviewed. If needed, additional bottles of N115 nasal spray will

be delivered to the patient in the clinic or via currier.

This process of testing every two days will continue until the particular subject proves to be virus free (2 Log or greater decrease in viral RNA or less than 1000 viral RNA copies) or 14 days, whichever is first. When the patient is virus free, he/she will be excused from the study. If the subject is virus free, they will be asked to provide a second nasal swab within 24 hours to verify the negative result.

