8.2 Testing Schedule-Sub-Chronic Phase of COVID-19 or flu positive patients

12.0 Safety Testing

12.1 Physical Exam

12.2.1 Nasal swab test for COVID-19 or influenza virus analyzed by qPCR.

13.0 A description of clinical procedures, laboratory tests, or other measures to be taken to monitor the effects of the drug in human subjects and to minimize risk

Tests and analyses will be conducted every other day during the study. If any aberrant values occur, the Clinical Coordinator will determine if that patient should continue the study or be removed. All aberrant values that occur during the study will be considered adverse events.

14.0. Safety Precautions Included in this Study:

The 20 mM nasal sodium pyruvate inhalation has been administered to both healthy humans and humans with lung diseases, without the occurrence of any SAE.

- First administration of nasal spray monitored via telehealth on in clinic.
- The initial nasal spray will be administered under the supervision of medical staff.

^{12.2} Efficacy Tests

• If a subject develops any adverse event during the follow-up period after study drug administration, the subject will be treated to a satisfactory resolution before being discharged from the clinic.

• Subjects will remain in contact via telehealth or in the clinic for 30 minutes after the initial inhalation of the nasal spray.

• Follow up telephone communications, as needed.

• If at any time the patient shows severe signs of disease or complications, they shall be removed from the study by the physician ([name]) and treated using proven methods for COVID19 or flu. These include, but are not limited to, antiviral drugs (Tamiflu, remdesivir, etc.), convalescent serum, oxygen and critical care. Treatment decisions will be made by [name], the patient's physician or an emergency care physician as needed. The patient may also withdraw from the study at any time, and for any reason, and seek traditional standard of care for COVID19 or flu.

• Severe signs of disease or complications include abnormal blood pressure (low or high), resting blood O₂ below 90%, apnea, fever over 103° F, altered mental state, impaired renal function, hemorrhaging or other severe symptoms.

15.0 Product Evaluation Questionnaire. This information will not be collected in the current study as it has been collected in numerous prior studies.

16.0 Daily Data Logbook:

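### Section 14.0 takes severely ill patients out of the study, not only off the spray, so their duration of infection (the primary outcome) will generally go unobserved

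*Combined protocol and SAP*

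**What the plan says.** The primary objective (5.3) is to evaluate N115 "by determining changes in the duration of an active infection by PCR from nasal". That duration is read from study swabs. Section 7.3.3 says "At home or on-site follow-up visits will occur every two days after Study Visit 1", with a swab at each, and "This process of testing every two days will continue until the particular subject proves to be virus free" or day 14 is reached. A negative result is to be confirmed: "If the subject is virus free, they will be asked to provide a second nasal swab within 24 hours to verify the negative result".

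Two rules can end this early.

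- Section 14.0 is mandatory: "If at any time the patient shows severe signs of disease or complications, they shall be removed from the study by the physician". Its triggers include abnormal blood pressure with no threshold, resting oxygen below 90%, fever over 103° F and other severe symptoms. The patient is then treated with established care, including antivirals.
- Section 13.0 is discretionary. For any aberrant value, "the Clinical Coordinator will determine if that patient should continue the study or be removed".

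Neither rule offers a third course, stopping the spray while the swabs go on.

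On data already in hand the plan is clear. Section 7.1 says "The data from all subjects that have been given a study compound will be retained for analysis" and "Details of the reason(s) why a subject is dropped from the study will be documented", and 9.0 says that data from withdrawn patients are analysed. Section 18.4 separates the intervention from follow-up. It does so as something the investigator may offer a withdrawing subject, it gives chart-review information as its example, and it needs consent. Section 18.2 names repeated-measures ANOVA and significance tests, with no rule for a duration that was cut short.

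**The concern.** The patients who leave under 14.0 are not a random subset. They have not yet cleared and they are severely ill. If severe illness goes with slow clearance (an assumption; the documents do not say), the missing durations are mostly long ones. The group that loses more patients then looks faster than it was. More removals on placebo would hide part of a real benefit; more removals on N115 would exaggerate a benefit or create one. Each group has 15 patients per virus, so each removal takes 1/15 = 6.7% of a group.

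**Working it through.** There is no figure in the plan to reproduce: it states no effect size, SD, removal rate or missing-data rule. The text can be checked directly; the size can only be illustrated.

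**Text.** The swabs are study procedures (7.3.3 and the testing schedule). Removal under 14.0 is from the study. No section continues the swabs after it. Sections 7.1, 9.0 and 18.4 keep what was collected, which shows that the patient had not cleared by the last swab but does not give the clearance day.

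**Inputs from the documents.** 15 per group per virus (6.1.1); swabs on days 2, 4, ..., 14; duration capped at day 14.

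**Assumed inputs.** Clearance time lognormal, log-SD 0.5, median 8 days on placebo; on N115 either 8 days (no effect) or 8 × 0.7 = 5.6 days (30% faster). Severity has correlation r with log clearance time. The most severe patients still uncleared are removed on day 2, 4 or 6.

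**Measure.** Difference D = mean placebo duration − mean N115 duration. With full follow-up and N115 30% faster, D = 2.14 days. The shift is D under the removal scenario minus D under full follow-up. Two ways of handling removed patients are shown: left out, or censored at the last positive swab (Kaplan-Meier restricted mean to day 14).

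| Scenario (placebo v N115 removed) | Handling | r = 0 | 0.3 | 0.5 | 0.7 |
|---|---|---|---|---|---|
| 15 v 15, 30% faster, 3 v 1 | left out | 2.05 | 1.90 | 1.79 | 1.67 |
| | censored | 2.15 | 1.98 | 1.86 | 1.75 |
| 15 v 15, 30% faster, 2 v 1 | left out | 2.12 | 2.03 | 1.97 | 1.92 |
| | censored | 2.14 | 2.04 | 2.00 | 1.93 |
| 15 v 15, no effect, 1 v 3 | left out | 0.11 | 0.26 | 0.36 | 0.49 |
| | censored | −0.01 | 0.15 | 0.26 | 0.39 |
| 30 v 30 pooled, 30% faster, 3 v 1 | left out | 2.10 | 2.01 | 1.96 | 1.90 |
| | censored | 2.14 | 2.05 | 1.99 | 1.93 |

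**Shifts for r = 0.3 to 0.7.**

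- 3 v 1: left out, 2.14 − 1.90 = 0.24 to 2.14 − 1.67 = 0.47 day; censored, 0.16 to 0.39 day.
- 2 v 1: left out, 0.11 to 0.22 day; censored, 0.10 to 0.21 day.
- 1 v 3 with no effect: a false N115 advantage of 0.26 to 0.49 day left out, 0.15 to 0.39 day censored.
- Pooled 30 v 30, 3 v 1: left out, 2.14 − 2.01 = 0.13 to 2.14 − 1.90 = 0.24 day; censored, 0.09 to 0.21 day.
- 1 v 1: D is 2.16 to 2.18 left out and 2.12 to 2.15 censored, a shift of at most 0.04 day.

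The standard error of D at 15 v 15 is about 1.2 days under these assumptions, so 0.5 day is about 0.5/1.2 = 0.4 of a standard error.

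**Cross-check with another model** (no drug effect, median 6 days, 20% slow clearers taking 1.5 to 3 times as long, removed patients left out). Removing half of the slow placebo patients and no N115 patients shifts the difference by 0.13 to 0.31 day. Removing all v half shifts it by 0.17 to 0.43 day. The extreme of all v none, about 0.20 × 15 = 3 v 0, shifts it by 0.31 to 0.72 day. Removing half in both groups gives none.

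**The remedy under the same test** (15 v 15, 30% faster, 3 v 1, all swabs continued, rescue shortening the remaining infection):

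| Rescue shortens by | r = 0 | 0.3 | 0.5 | 0.7 |
|---|---|---|---|---|
| 25% | 2.00 | 1.99 | 2.00 | 2.02 |
| 50% | 1.82 | 1.79 | 1.79 | 1.79 |

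The shift from 2.14 is 0.12 to 0.15 day at 25% and 0.32 to 0.35 day at 50%.

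Scoring removed patients as not cleared by day 14, with no effect on clearance and 3 v 1 removed, gives a false N115 advantage of 0.54/0.43/0.36/0.26 day for r = 0/0.3/0.5/0.7.

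**The case against.** **The size is small and assumed.** The documents give no removal rate. Entry excludes significant cardiac disease, recent hospitalisation for airway disease and an abnormal chest x-ray, so 3 of 15 in one group may not happen. Triggers such as abnormal blood pressure, and the aberrant values of 13.0, need not track slow clearance; at r = 0 the 3 v 1 shift is about 0.1 day left out and none censored. With 2 v 1 removals left out and no drug effect, the two-sided false-positive rate was 5.1 to 6.4%; only 1 v 3 at r = 0.7 reached 8.3%. This stands, and it limits the point to an inexpensive improvement.

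**Section 18.4 already allows follow-up.** It does, and its chart-review results are examples, not limits. A PCR result might be recovered that way, and the consent form, which was not available, may already cover it. But the offer is optional, is written for subjects who withdraw and not those the physician removes, and schedules no swabs to clearance.

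**Continued swabs are contaminated by rescue.** Section 14.0 expects antivirals, so this is the likely case. If rescue halves the remaining infection, the observed-swab difference is 1.79, against 1.98, 1.86 and 1.75 censored at r = 0.3, 0.5 and 0.7. That is further from 2.14 at the first two and only 0.04 day nearer at the third. With 25% rescue, continued swabs are level with censoring at r = 0.3 (1.99 v 1.98) and nearer above it. So the choice is partly about which effect to estimate. What favours continuing is that an analyst who has the later swabs can still censor them, while one without them cannot recover the clearance day.

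**Conclusion.** The point holds as a design weakness. Followed as written, 14.0 loses the primary outcome for a non-random group of patients, 13.0 can do the same at discretion, and 18.2 does not say how their durations are handled. The shift is about 0.1 to 0.5 day at 15 v 15, or about 0.1 to 0.2 day if both viruses are pooled and 3 v 1 are removed. These figures rest on the assumed removals, an assumed correlation of 0.3 to 0.7, and the assumed clearance distribution. With balanced removals there is essentially no shift.

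A reader might infer more, and the documents do not support it:

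- That the outcome is never observed for these patients. Section 18.4 leaves a route, though an unscheduled one.
- That removed patients would pass as cleared. The last titre, the documented reason and the lack of a confirming swab tell them apart.
- That everyone removed is severely ill. Section 13.0 is discretionary and covers any aberrant value.
- That the rule favours N115. The direction depends on which group loses more patients.
- That continued swabs would remove the bias. With strong rescue they do not.

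**What to change.** **Sections 14.0 and 13.0.** Replace removal from the study with *taken off the study spray and treated*. Continue the scheduled swabs and vital signs to clearance or day 14 if the patient agrees. Put this in the original consent form, if it is not already there, so that 18.4 does not call for a second consent.

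**Section 18.2.**

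- Analyse every such patient in the assigned group with the observed swabs, and describe the result as the effect of the assigned spray plus any rescue treatment.
- Never score a last positive swab as clearance.
- Report an analysis censored at spray stop or rescue as a sensitivity analysis.
- Report not cleared by day 14 as a further sensitivity analysis only, because it is a composite that penalises the group with more severe patients.

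**Cost.** Some wording, possibly a consent change, and at most seven scheduled swabs (days 2 to 14) plus one confirming swab per affected patient. Home visits are already allowed (7.3.3), but some swabs will be missed in hospital. Later swabs reflect rescue antivirals: if these halve the remaining infection, the observed-swab result shifts by 0.3 to 0.4 day under 3 v 1 removals, which is why the censored analysis must stand beside it.

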18.0 Study Management

18.1 Case Report Forms

Case Report Forms (CRF) will be supplied by Cellular Sciences and the testing facility. Data will be recorded in the CRFs according to the following:

Instructions to data entry personnel and Monitor:

(a)Explain all missing data and include reference to any original data that is not contained in the study file. If a space is blank because the item was not done, mark the item "N/A". If the item is not applicable to the individual case, mark the item "N/A". If an item is unknown, mark the space "UNK". Legibly write or print all entries in black ink. If an entry error has been made, draw a single straight line through the wrong entry and enter the correct data above it. Please initial and date all such changes. DO NOT ERASE OR OPAQUE OUT ERRORS. For clarification of illegible or uncertain entries, print the clarification above the item, then initial and date the clarification.

18.2. Data Collection, Management, and Statistical Analysis

The data management staff at the research clinic and lab (Trinity Healthcare and Dynamic DNA Labs) will collect and manage the data. Monitoring and auditing of the data will be

conducted by a staff member of Cellular Sciences remotely.

The basic statistical analysis will be repeated measurements of Analysis of Variance using baseline measurements as a covariant per subject. Group comparisons of N115 to placebo will be analyzed by ANOVA followed by Chi Square, Fisher Exact, and other appropriate significance tests. Data will be compared to placebo controls and current publicly available matched data and observed values compared. Time dependence in viral titer reduction will also be compared. [name] will be responsible for the statistical analysis. Analysis will be performed blinded.

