7.3.5. Products Description (How Administered)

The product is an all-natural patented 20 mM sodium pyruvate in 0.9% sodium chloride nasal spray solution with 0.02% benzalkonium chloride as a preservative. The plastic bottle contains 30 mL. It is non-steroidal. Patients will forcibly expel air from their lungs and then will administer three sprays per nostril while inhaling strongly so that the drug is transported through the nose and into the lungs. The drug is to be administered three times per day (morning, mid-day, and evening). The product comes with instructions for administration (three sprays per nostril).

7.4 Concomitant Therapy

No concomitant therapy is prescribed for this study, but the subjects may continue to use their normal therapy as long as they list it as a current medication. The Principal Investigator may prescribe "rescue medication" should it be required by any of the patients. Patients may continue taking nutritional supplements. safety. Subjects may not use any of the following during the trial or for one week before enrollment in the trial: all intranasal medications or lavages, antihistamines, steroids or anti-inflammatory medications of any kind. Subjects also may not currently be taking any antiviral or antibiotic medications.

8.0. The Method For Determining The Dose(S) To Be Administered, The Planned Maximum Dosage, And The Duration Of Individual Patient Exposure To The Drug.

This is a constant dose study. The amount of delivered sodium pyruvate was determined in clinical trials to be three sprays of 20 mM sodium pyruvate in 0.9% sodium chloride solution per nostril, and this is repeated 3x per day (morning, midday, and evening). The dose was determined by evaluating the data from both animal and human studies (cited above).

9.0. A Description Of The Observations And Measurements To Be Made To Fulfill The Objectives Of The Study.

Observations for safety will include a pregnancy test for women of child-bearing age, blood oximetry, and vital signs.

Observations for efficacy will include evaluation of sore throat, congestion, erythema, the number of daily coughs, and flu-like symptoms. Perceived adverse events will be monitored.

Premature Withdrawal

The patients can withdraw from the study at any time, and for any reason. All data collected from these patients will be analyzed. Reasons for withdrawal will be recorded to ensure that it was not due to an adverse event.

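### The primary objective is duration of PCR-positive infection, but section 18.2 assigns no test to duration, names no primary test, and gives no rule for patients without confirmed clearance

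*Combined protocol and SAP*

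**What the plan says.** **Objective.** Section 5.3 gives the primary objective as an evaluation of N115 by "determining changes in the duration of an active infection by PCR from nasal" samples. It speaks of an objective; no section formally labels an endpoint.

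**Measurement.** Sections 5.4 and 7.3.3 schedule a swab every two days until the patient is negative (a 2-log fall, or fewer than 1000 RNA copies) or reaches 14 days. Section 7.3.3 then says "When the patient is virus free, he/she will be excused from the study". The next sentence adds that such patients "they will be asked to provide a second nasal swab within 24 hours to verify the negative result". It does not say what follows if that second swab is positive.

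**Analysis.** Section 18.2 gives the basic analysis as "The basic statistical analysis will be repeated measurements of Analysis of Variance using baseline measurements as a covariant per subject". It continues: "Group comparisons of N115 to placebo will be analyzed by ANOVA followed by Chi Square, Fisher Exact, and other appropriate significance tests". The only outcome it names is titre: "Time dependence in viral titer reduction will also be compared". No method goes with that sentence.

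**Viral-load purpose.** The list under Purpose and Objectives of the Studies asks how fast viral load and infection fall relative to Day 0, historical data and placebo. Section 3.0 asks whether viral loads are reduced or eliminated.

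**Incomplete patients.** Section 7.1 says "The data from all subjects that have been given a study compound will be retained for analysis". The Premature Withdrawal paragraph says "All data collected from these patients will be analyzed". Section 18.4 keeps data collected before withdrawal. Section 14.0 removes patients who show severe signs of disease.

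**The concern.** Duration is one number per patient: the time to clearance. It is known only to within a two-day swab interval and cut off at Day 14. A repeated-measures model needs a series per patient, so the basic analysis cannot report how many days N115 takes off an infection. It can address titre, but section 7.3.3 ends the titre series at clearance. If N115 works, its patients leave the series sooner, and those left in both arms are the slow clearers.

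One-way ANOVA on durations is a permitted reading of section 18.2. It would address the objective, but each patient would need a duration, and none is defined for those who have not cleared.

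Several analyses therefore fit the text, and nothing says which one decides the trial. The choice could be made after results are seen. Blinded analysis does not prevent this: it hides which arm is which, not which test gives the smallest p-value.

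**Working it through.** **1. Text check.** Four outcome groups appear in the protocol: duration (5.3), viral load (Purpose and Objectives; 3.0), symptoms and vital signs (5.3 secondary; 9.0). Four named procedures appear in 18.2: repeated-measures ANOVA, ANOVA, chi-square and Fisher exact, plus an open remainder. No sentence pairs a procedure with duration, and none is called primary. Sections 7.1, 18.4 and Premature Withdrawal settle whose data are kept. None gives a censoring time or an assigned value. There is no planned effect, variance, alpha or power to reproduce; section 6.1.1 gives only 15 per arm for each virus.

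**2. What the exit rule does to a titre analysis (assumed inputs).** Baseline log10 RNA has mean 7, SD 1.5, floored at 3.5. Placebo decay is 0.3, 0.45 or 0.7 log/day, log-normal with CV 40%. N115 decay is 1.5 times faster. Swab SD is 0.5. Swabs are on Days 0, 2, ..., 14 with the section 7.3.3 stopping rule; 200,000 patients per arm. Removals are not simulated.

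| Placebo decay (log/day) | 0.3 | 0.45 | 0.7 |
|---|---|---|---|
| Still swabbed at Day 6, placebo / N115 | 79% / 57% | 57% / 28% | 26% / 7% |
| Swabbed at every visit to Day 14, placebo / N115 | 9.4% / 1.6% | 1.6% / 0.1% | 0.1% / <0.01% |
| Day 6 contrast, swabbed as share of all patients, no assay floor | 54% | 35% | 20% |
| The same, 100-copy floor | 59% | 48% | 48% |
| Difference in mean days to first negative, capped at 14 | 2.0 | 1.5 | 1.1 |

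The share is (N115 minus placebo change from Day 0 among patients still swabbed) / (the same difference among all patients), taken before rounding. For the fastest decay it is -0.42 / -2.09 = 0.20 with no floor, and -0.39 / -0.81 = 0.48 with a 100-copy floor. At Day 2 it is 100%, because everyone is still swabbed.

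A complete-case analysis over all visits would have at most 15 x 0.094 = 1.4 placebo and 15 x 0.016 = 0.2 N115 patients.

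**3. How much the missing scoring rule matters.**

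*Fast clearance (kinetics of step 2).* Uncleared at Day 14 are at most 4.8% of placebo (15 x 0.048 = 0.7 patients) and 0.6% of N115. In that slowest-decay case the difference is 2.0 days with uncleared patients scored 14, 2.1 with them scored 16, and about 1.7 with them dropped. In the fastest-decay case all three give 1.06.

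*Slower clearance (assumed).* Exponential clearance, placebo median 5, 7 or 10 days, hazard ratio 1.5 or 2, 10% at risk of removal at a uniform time before Day 14. The true difference is in mean days to first negative swab, capped at 14, had nobody been removed.

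| Median, HR | True (days) | Uncleared and removed dropped | Last-swab value | Both scored 14 |
|---|---|---|---|---|
| 5, 1.5 | 1.51 | 0.83 (55%) | 1.41 | 1.49 |
| 5, 2 | 2.46 | 1.46 (59%) | 2.31 | 2.44 |
| 7, 1.5 | 1.55 | 0.67 (43%) | 1.45 | 1.52 |
| 7, 2 | 2.62 | 1.24 (47%) | 2.45 | 2.57 |
| 10, 1.5 | 1.43 | 0.50 (35%) | 1.33 | 1.39 |
| 10, 2 | 2.53 | 0.97 (38%) | 2.36 | 2.46 |

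Here 13-34% of placebo patients are uncleared at Day 14. Dropping them does the damage; either assigned value stays within about 7% of the true difference.

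**4. Power.** Under the step 2 kinetics, log-rank has 43-46% and ANOVA on capped durations 42-46% at 15 per arm; both have 73-75% at 30 per arm.

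**The case against.** The strongest defence is that section 18.2 is less mismatched than it looks. The protocol states a viral-load purpose, and repeated measures with a baseline covariate fits it. ANOVA on durations is also open to the analyst, with the same power as log-rank. Data from treated and withdrawn patients are expressly kept. Section 18.2 does not prescribe a complete-case or visit-by-visit analysis, so the 20-60% figure describes one possible implementation, under assumed decay rates and assay floors. Under fast clearance the scoring rule hardly matters.

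Most of this stands, and it limits the point. A reader might infer that the plan excludes withdrawn patients, that its titre analysis will necessarily lose 40-80% of the effect, or that ANOVA costs power. The documents and the calculations support none of these.

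Two things remain. Section 5.3 ranks duration first, and section 18.2 does not follow that ranking. Keeping a patient's data does not say what duration an uncleared patient contributes. The trial cannot know in advance whether clearance will be fast enough for that not to matter.

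**Conclusion.** The concern holds and should be fixed before unblinding: the plan has no designated analysis for its own primary objective. This rests on the text alone and on no assumed number.

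The sizes are illustrations, because the documents give no clearance rates. If titre were analysed by complete cases or visit by visit, a real benefit would tend to be understated, with about 20-60% of the all-patient contrast visible at Day 6 under the assumed kinetics. A likelihood mixed model would lose much less. The effect of the missing scoring rule runs from slight (at most about 5% of placebo uncleared) to large (35-60% of the true difference kept), and the large end applies if uncleared and removed patients are dropped. Removal related to treatment or prognosis was not modelled.

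**What to change.** Rewrite section 18.2 before unblinding as follows.

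- Name one primary analysis: time from Day 0 to the first negative nasal swab as defined in section 7.3.3, N115 versus concurrent randomised placebo, by log-rank or an interval-censored equivalent. Patients uncleared at Day 14 are censored at Day 14.
- State whether it is run within each virus cohort of section 6.1.1 or pooled and stratified by virus.
- State one analytic rule for removed and withdrawn patients, for example counted as not cleared through Day 14. Use the alternative, censoring at the last swab, as a sensitivity analysis.
- State how an unconfirmed negative is counted, and reconcile the section 7.3.3 sentences on excusing the patient and on the second swab.
- Make serial titre secondary, by a likelihood mixed model on log10 copies.
- Remove the open-ended last item in the list of tests for the primary claim.

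The essential repair is one named outcome, one named test and the handling rules. Log-rank is recommended because it handles uncleared patients directly, not because it adds power. The cost is a rewritten section 18.2, a clarifying sentence in section 7.3.3 and a little more analysis work. The primary analysis uses swabs already scheduled.
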